1 BACKGROUND AND RATIONALE

1.1 INTRODUCTION

IPI-145 is a potent phosphoinositide-3-kinase (PI3K)- δ, γ inhibitor being developed by Verastem, Inc. (Verastem). PI3K- δ and PI3K- γ isoforms are necessary for adaptive and innate immunity, and are important mediators in inflammatory disorders and hematologic malignancies. Therefore, IPI-145 is being developed as an orally administered potential therapeutic in hematologic malignancy and inflammatory disease indications. This study is an evaluation of IPI-145 in iNHL subjects whose disease is refractory to rituximab and to either chemotherapy or radioimmunotherapy (RIT).

1.2 BACKGROUND

1.2.1 Functions of PI3K- δ and PI3K- γ

There are four mammalian isoforms of class 1 PI3Ks: PI3K- α, β, δ (class 1a PI3Ks) and PI3K- γ (a class 1b PI3K). These PI3Ks catalyze the production of phosphatidylinositol (3,4,5)-trisphosphate (PIP3), leading to activation of the downstream effector pathways important for cellular survival, differentiation, and function. PI3K- α and PI3K- β are widely expressed, and are important mediators of signaling from cell surface receptors. PI3K- α is the isoform most often found mutated in cancers, and has a role in insulin signaling and glucose homeostasis.^{2,3} PI3K- β is activated in cancers where phosphatase and tensin homolog (PTEN) is deleted. Both isoforms are targets of small molecule therapeutics in development for cancer. PI3K- δ and PI3K- γ are preferentially expressed in leukocytes, and are important in leukocyte function.

PI3K- δ is activated by cellular receptors (e.g., receptor tyrosine kinases) through interaction with the SH2 domains of the PI3K regulatory subunit (p85), or through direct interaction with RAS.

PI3K- γ is associated with G-protein coupled receptors (GPCRs), is responsible for the very rapid induction of PIP3 in response to GPCRs, and can be also activated by RAS downstream of other receptors. PIP3 produced by PI3K activates effector pathways downstream through interaction with pleckstrin homology (PH) domain containing enzymes (e.g., PDK-1 and AKT [PKB]).⁴

It is clear that both PI3K- δ and PI3K- γ isoforms are important for chemotaxis and cell migration, and have independent roles in models of inflammatory diseases.⁵ The roles of PI3K- δ and PI3K- γ in different immune cell types are outlined below.

B-Cells

PI3K- δ is important in B-cell function including development, activation, chemotaxis, migration, and homing to lymphoid tissue, and inhibitors of PI3K- δ block these functions.^{3, 4, 6-12}

T-Cells

In T-cells, PI3K- δ has demonstrated a role in receptor and cytokine signaling. PI3K- δ is important for T-cell function including proliferation, activation, and differentiation.^{3, 13-21}

Neutrophils

PI3K- δ along with PI3K- γ , are important in the response to immune complexes and FC γ RII signaling in neutrophils, including migration, and the neutrophil respiratory burst. PI3K- γ is also critical for the migration and function of tumor associated neutrophils, suggesting a role in tumor immunity and cancer progression.²² As such, PI3K- δ and PI3K- γ are central mediators of autoimmune disease and cancer.²³⁻²⁷

Macrophages/Monocytes

In macrophages collected from patients with chronic obstructive pulmonary disease (COPD), glucocorticoid responsiveness can be restored by treatment of the cells with inhibitors of PI3K- δ . Macrophages rely on PI3K- δ and PI3K- γ for responses to immune complexes through the Arthus reaction (FC γ R and C5a signaling).^{26, 28, 29} PI3K- γ is also critical for the migration and function of tumor associated macrophages suggesting a role in tumor immunity and cancer progression.²²

Mast Cells

In mast cells, stem cell factor- (SCF) and IL-3-dependent proliferation, differentiation and function are PI3K- δ and PI3K- γ dependent, as is chemotaxis. The allergen/IgE cross-linking of FCeR1 resulting in cytokine release and mast cell degranulation is inhibited by treatment with PI3K- δ inhibitors, suggesting a role for PI3K- δ in allergic disease.³⁰⁻³²

NK Cells

Natural killer (NK) cells are dependent on both PI3K- δ and PI3K- γ for efficient migration. NK cell activity against viral targets is impaired in PI3K- δ kinase-dead mice, while the activity against tumors is unaffected.³³⁻³⁶

1.2.2 Indolent non-Hodgkin Lymphoma

Non- Hodgkin lymphoma (NHL) is the seventh most common cancer in male and female adults in the US,³⁷ representing the ninth and sixth leading cause of cancer deaths for men and women, respectively.³⁷ In Europe, it is the eighth most commonly diagnosed cancer, and the tenth most common cause of death from cancer in adults. The majority (>90%) of NHL represents malignancies of B-lymphocyte lineage and express CD20. There are approximately 14 classes of indolent and aggressive B-cell lymphoma classified according to morphology, immunophenotyping, genetics and clinical factors.³⁸ The most common of the indolent B-cell lymphomas is follicular lymphoma, comprising approximately 22% of all B-cell lymphomas. Less common are small lymphocytic lymphoma (SLL, approximately 6%), and marginal zone B-cell lymphoma, malt-type or nodal-type, approximately 5% and 1% of all B-cell lymphomas, respectively.

Indolent lymphomas tend to grow slowly. Even without treatment, subjects with indolent lymphoma often live for many years without major problems from their disease. For some subjects, no treatment is recommended until symptoms develop. With treatment, the expected median survival time is approximately 8 to 10 years. Overall response rates of $\geq 80\%$ can be

**Protocol IPI-145-06
IPI-145****Verastem, Inc.**

expected with initial treatment. However, indolent lymphoma is considered incurable and almost all patients relapse with the response and duration of response to subsequent therapies decreasing with each line of therapy.^{39, 40}

Rituximab, an anti-CD20 therapy, is commonly used as a single agent or in combination with cytotoxic chemotherapy for the treatment of B-cell NHL. The addition of polychemotherapy regimens to rituximab treatment has resulted in greater disease responses and longer duration of response in first-, second-, and later lines of therapy. However, there is an increasing need for effective treatments for patients with iNHL who, due to the incurable nature of this disease, eventually develop disease refractory to treatment with rituximab and chemotherapy. No standard of care exists in the refractory setting, with the treatment regimen primarily being determined by prior therapies. Therapies utilized in the refractory setting include additional chemotherapy, stem cell transplantation, and RIT. However, all these therapies are associated with lower response rates in patients refractory to chemotherapy and rituximab. In addition, stem cell transplantation is associated with significant toxicity, especially in elderly patients or those patients with comorbidities. RIT is associated with significant myelosuppression. Patients whose iNHL has not responded or has progressed within 6 months of either a rituximab containing chemotherapy regimen or RIT represent a population which would benefit from the development of novel anticancer agents.

1.3 IPI-145**1.3.1 IPI-145, a Potent PI3K- δ, γ Inhibitor**

PI3K- δ and PI3K- γ contribute to the development and maintenance of inflammatory and autoimmune diseases, and hematologic malignancies.^{3, 4, 8, 41} IPI-145 is a potent PI3K- δ, γ inhibitor being developed as a potential therapeutic in hematologic malignancy and inflammatory disease indications.

1.3.2 Non-Clinical Summary of IPI-145

See the IPI-145 Investigator's Brochure for detailed summaries on pharmacology, toxicology, and absorption, distribution, metabolism, and excretion (ADME) of IPI-145.

1.3.3 Clinical Experience in Humans**1.3.3.1 Study IPI-145-01 (Phase 1, first in human study)**

Study IPI-145-01 was a randomized, double-blind, placebo-controlled, Phase 1 study in healthy adult subjects. Study objectives were to evaluate the safety, tolerability, PK and pharmacodynamics (PD) of single and multiple ascending doses of IPI-145 and to assess the effect of food and ketoconazole on the PK of IPI-145. This study is complete and data are summarized below.

One-hundred and six (106) subjects were enrolled overall, which included 36 subjects in the single ascending dose (SAD) portion (24 active treatment; 12 placebo), 48 subjects in the multiple ascending dose (MAD) portion (36 active treatment; 12 placebo), 6 subjects in the food effect (FE) effect portion (consisting of IPI-145 dosing with sequential fed and fasting portions),

Protocol IPI-145-06**Verastem, Inc.****IPI-145**

and 16 subjects in the drug-drug interaction (DDI) portion (consisting of IPI-145 dosing periods with and without ketoconazole). The total subject exposure to IPI-145 is summarized in [Table 5](#).

Table 5: Subject Exposure (Study IPI-145-01)

PART	Treatment Exposure	Duration of Treatment	Total Exposure per Subject (mg)	Total No. of Subjects Exposed
SAD	Placebo SD	1 day	0	12
	1 mg IPI-145 SD	1 day	1	4
	2 mg IPI-145 SD	1 day	2	4
	5 mg IPI-145 SD	1 day	5	4
	10 mg IPI-145 SD	1 day	10	4
	20 mg IPI-145 SD	1 day	20	4
	30 mg IPI-145 SD	1 day	30	4
MAD	Placebo Q12h or Q24h	14 days	0	12
	1 mg IPI-145 Q12h*	14 days	26	9
	2 mg IPI-145 Q12h*	14 days	52	9
	5 mg IPI-145 Q12h*	14 days	130	9
	10 mg IPI-145 Q24h	14 days	140	9
FE	25 mg IPI-145 Fasted-Fed	2 days	50	3
	25 mg IPI-145 Fed-Fasted	2 days	50	3
DDI	10 mg IPI-145 SD	2 days	20	16

SD = single dose; Q12h = once every 12 hrs; Q24h = once every 24 hrs; SAD = single ascending dose; MAD = multiple ascending dose; FE = food effect; DDI = drug-drug interaction. *includes QD dosing on Days 1 and 14.

IPI-145 was well tolerated at the doses evaluated. There were no deaths and no serious adverse events (SAEs). Dose escalation proceeded as planned in both the SAD and MAD portions, to a pre-determined exposure limit based on the findings in the 28-day nonclinical toxicology study in rats.

No clinically significant safety laboratory or ECG abnormalities were observed during any portion of the study.

Pharmacokinetic assessments demonstrated that IPI-145 is rapidly absorbed following single and multiple dose oral administration, with the maximum plasma concentration observed typically 1 hr after dosing. Across the dose ranges evaluated, IPI-145 exposure increased proportionally to dose. The mean elimination half-life ranged from 6.5 to 11.7 hr after repeat dosing and did not depend on the dose level administered. IPI-145 accumulation was less than 2-fold following 14 days of Q12 hr oral administration.

Data from the DDI portion indicated that concomitant administration of 200 mg Q12hr ketoconazole increased exposure to IPI 145. On average, C_{max} , $AUC_{0\text{-last}}$ and $AUC_{0\text{-inf}}$ increased

by approximately 66%, 285% and 295%, respectively, in the presence of ketoconazole compared to IPI-145 administered alone.

See the IPI-145 Investigator's Brochure for further information.

1.3.3.2 *Study IPI-145-02 (Phase 1, Hematologic Malignancies)*

A Phase 1 dose-escalation study (IPI-145-02) to evaluate the safety, PK and biological activity of orally administered IPI-145 in subjects with advanced hematologic malignancies is currently ongoing. Sequential cohorts of subjects have been enrolled at progressively higher dose levels (ranging from 8 mg to 100 mg given orally BID continuously in 28-day cycles) with expansion cohorts of subjects with select hematologic malignancies. Dose limiting toxicities (DLTs) of Grade 3 rash and Grade 3 alanine aminotransferase (ALT)/aspartate aminotransferase (AST) elevations were experienced by two subjects receiving 100 mg BID. Therefore, the maximum tolerated dose (MTD) has been determined to be 75 mg BID.

Clinical Safety

A total of 193 subjects have been enrolled in study IPI-145-02 as of 28 October 2013. Of these, 32 (17% of enrollment) are iNHL subjects (including follicular and marginal zone lymphoma subtypes). Other populations include relapsed/refractory chronic lymphocytic leukemia/small lymphocytic leukemia (CLL/SLL), n=52 (27%), treatment-naïve CLL, n=15 (8%) and other diagnoses, n=109 (56%).

Across the population of subjects enrolled, 122 are male and 71 female with a median age of 66 years. IPI-145 doses administered include 8 mg BID (n=1), 15 mg BID (n=6), 25 mg BID (n=61), 35 mg BID (n=3), 50 mg BID (n=3), 60 mg BID (n=4) 75 mg BID (n=112), and 100 mg BID (n=3). Subjects with iNHL were enrolled at 15 mg BID (n=1), 25 mg BID (n=15), 50 mg BID (n=1) and 75 mg BID (n=15).

As of 28 October 2013, across all subjects in all dose cohorts, the median number of treatment cycles was 4.1 cycles, with 42% of subjects continuing on treatment. Subjects who received 25 mg BID had a median time on treatment of 4.7 cycles.

Subjects with iNHL (n=32) had a median 8.5 cycles of treatment (range 0.1 to 22.7 cycles) and subjects dosed with 25 mg BID had a median of 9.8 cycles of treatment (range: 0.1 to 20.7 cycles).

In all subjects across all dose cohorts, treatment-emergent adverse events (TEAEs) have occurred in 180 (93%) subjects, including 56 subjects (92%) in the 25 mg BID dose group. The most common TEAEs ($\geq 20\%$) in all dose groups combined included fatigue (32%), ALT or AST increased (combined, 32%), diarrhea (27%), pyrexia (25%), nausea (24%), cough (22%) and neutropenia (20%). Related Grade ≥ 3 TEAEs occurred in 102 subjects (53%). The most common related Grade ≥ 3 TEAEs ($\geq 5\%$) included ALT or AST increased (combined, 16%), neutropenia (13%) and neutrophil count decreased (5%).

Across all 32 iNHL subjects, TEAEs have occurred in 31 (97%) subjects. The most common TEAEs ($\geq 20\%$) in all dose groups combined included: ALT or AST increased (combined, 53%), pyrexia (41%), rash (combined terms, 41%), fatigue (34%), diarrhea (34%), nausea (34%), neutropenia (31%) and cough (31%). Related Grade ≥ 3 TEAEs occurred in 22 subjects (69%). The most common related Grade ≥ 3 TEAEs ($\geq 5\%$) included: ALT or AST increased (combined,

Protocol IPI-145-06**Verastem, Inc.****IPI-145**

34%), neutropenia (25%), diarrhea (16%), anemia (9%), febrile neutropenia (9%), neutrophil count decreased (6%) and pneumonitis (6%).

In iNHL subjects in the 25 mg BID group, TEAEs have occurred in 15 subjects (100%). The most common TEAEs ($\geq 20\%$) included: ALT or AST increased (combined, 53%), nausea (40%), rash (combined terms, 27%), vomiting (27%), diarrhea (27%), neutropenia (27%), pyrexia (20%), fatigue (20%) and cough (20%). Related Grade ≥ 3 TEAEs occurred in 11 (73%) of iNHL subjects in the 25 mg BID group. The most common related Grade ≥ 3 TEAEs ($\geq 5\%$) included: ALT or AST increased (combined, 40%).

Preliminary PK data from Study IPI-145-02 demonstrate IPI-145 is rapidly absorbed following oral dosing in subjects with advanced hematologic malignancies, with the maximum plasma concentration (C_{max}) generally achieved at approximately 1 hour post-dose. Steady state exposure over the dosing interval (AUC_{0-12}) is proportional to dose. Following repeat dose administration of 25 mg BID, mean C_{max} and AUC_{0-12} values are 1460 ng/mL and 8129 ng*h/mL, respectively. IPI-145 elimination half-life ($t_{1/2}$) does not appear to vary with dose and the mean $t_{1/2}$ was 4.5 hours following 25 mg BID administration.

1.4 RATIONALE FOR IPI-145 AS A POTENTIAL THERAPY FOR SUBJECTS WITH INDOLENT NHL

PI3K- δ and PI3K- γ are expressed in hematopoietic cells, and are critical for the ability of normal immune cells to respond to survival and differentiation signals in their environment. In cancer patients, where the pathways mediated by PI3K- δ, γ contribute to survival, proliferation, and differentiation of cancer cells, treatment with IPI-145 may be beneficial. The tumor microenvironment plays an important role in the development and maintenance of cancer cells.⁴² Cancer cells through the expression of various cytokines, growth factors, and chemokines recruit multiple cell types including myeloid cells capable of differentiating into tumor-associated macrophages (TAMs) which promote angiogenesis and augment tumor growth.⁴³ Therefore, agents that target TAMs as well as other types of infiltrating leukocytes are of potential therapeutic interest in oncology.

PI3Ks play pivotal roles in cell signaling and regulate a variety of cellular functions relevant to oncogenesis. Impaired development and function of B and T lymphocytes has been demonstrated in PI3K- δ and PI3K- γ isoform knockout mice, supporting the development of PI3K- δ, γ specific inhibitors for B- and T-cell lymphoid malignancies.

1.5 DETERMINATION OF STARTING DOSE AND REGIMEN

In Study IPI-145-02, responses (CR and PR) have been observed in subjects with iNHL at doses ≤ 25 mg BID. Overall, as of 28 October 2013, 193 subjects have been dosed with IPI-145, including 32 subjects with iNHL. Of the 32 iNHL subjects, 15 have been dosed with IPI-145 at 25 mg BID, with a median time on treatment of 4.7 cycles.

The clinical safety data as of 28 October 2013 for patients on 25 mg BID in the overall population (n=61) and in the iNHL population (n=15) suggest this dose is well tolerated with a safety profile similar to what might be expected in patients with advanced hematologic malignancies. Frequently occurring adverse events ($\geq 20\%$) in the iNHL population receiving 25 mg BID included ALT or AST increased (combined terms) (53%), nausea (40%), rash (combined terms, 27%), vomiting (27%), diarrhea (27%), neutropenia (27%), pyrexia (20%), fatigue (20%) and cough (20%). Among the 29 evaluable subjects with iNHL, the best ORR was 62% (3 CR, 15 PR) with 8 SD and 2 PD. The overall response rate was 67% for subjects who received ≤ 25 mg BID and 57% for subjects who received > 25 mg BID. The median time to response was 1.8 months (range: 1.5 to 4.1), with no variation between dose groups.

Based on the safety and clinical activity of IPI-145 observed to date in Study IPI-145-02, a dose of 25 mg BID has been selected to evaluate in iNHL patients in the Phase 2 setting.

1.6 SUMMARY

Effective treatment for patients who have been diagnosed with iNHL who have not responded to or have progressed within 6 months of a rituximab containing chemotherapy regimen or RIT is an area of high unmet medical need. IPI-145 is a potent PI3K- δ, γ inhibitor being developed as a potential therapeutic in hematologic malignancy and inflammatory disease indications. Initial experience of IPI-145 in the treatment of patients with relapsed/refractory iNHL suggests a therapeutic potential for IPI-145 in high risk iNHL.

Protocol IPI-145-06

IPI-145

Verastem, Inc.

Therefore, Verastem, Inc. is conducting a Phase 2 clinical trial to evaluate the safety and efficacy of IPI-145 as a monotherapy in subjects with iNHL that is refractory to rituximab and to either chemotherapy or RIT.

2 STUDY OBJECTIVES

2.1 PRIMARY OBJECTIVES

The primary objective of this trial is to evaluate the antitumor activity of IPI-145 administered to subjects diagnosed with iNHL (defined as FL, MZL [splenic, nodal and extranodal], or SLL) whose disease is refractory to rituximab and to either chemotherapy or radioimmunotherapy (RIT).

2.2 SECONDARY OBJECTIVES

The secondary objectives of the study are:

- To evaluate the safety of IPI-145 in all subjects
- To evaluate additional efficacy parameters in all subjects
- To evaluate the PK of IPI-145 and, if applicable, its metabolite(s)

2.3 EXPLORATORY OBJECTIVES

The exploratory objectives of the study are:

- To evaluate whether baseline values or treatment-related changes in biomarkers correlate with IPI-145 clinical activity, safety and/or resistance in iNHL.
- To evaluate whether tumor genomic or pharmacogenomic markers correlate with IPI-145 clinical activity, safety, PK and/or resistance in iNHL
- To evaluate the health-related quality of life (QoL) of subjects

3 STUDY ENDPOINTS

3.1 PRIMARY ENDPOINT

The primary endpoint of the study is the Overall Response Rate (ORR), with overall response defined as best response of complete response/remission (CR) or partial response/remission (PR) according to the revised International Working Group (IWG) Criteria¹

3.2 SECONDARY ENDPOINTS

The secondary endpoints of the study are:

- Treatment-emergent adverse events (TEAEs), ECG measures, and changes in safety laboratory values
- Duration of response (DOR) defined as the time from the first documentation of response to the first documentation of progressive disease (PD) or death due to any cause
- Progression-free survival (PFS) defined as the time from the first dose of study treatment to the first documentation of PD or death due to any cause
- Overall survival (OS) defined as the time from the first dose of study treatment to the date of death
- Time to response (TTR), defined as the time from the first dose of study treatment to the first documentation of response (complete or partial)
- PK parameters derived from plasma IPI-145 concentrations and, if applicable, its metabolite(s)

3.3 EXPLORATORY ENDPOINTS

The exploratory endpoints of the study are:

- Lymph node response rate (LNR rate), with LNR defined as $\geq 50\%$ reduction in the Sum of the Products of the Perpendicular Diameters (SPD) of nodal target lesions
- Serum, plasma and tissue biomarkers, and blood immunophenotype
- Germline DNA sequence variations
- Tumor genomic features (e.g. DNA sequence variation, DNA copy number variation, and/or RNA expression)
- Health-related QoL of subjects as assessed by the following subject-reported questionnaire:
 - EuroQol-5D (EQ-5D), a standardized instrument for use as a measure of health-related QoL

4 STUDY DESIGN

This is an open-label, single arm efficacy and safety study of IPI-145 administered orally to subjects who have been diagnosed with iNHL (FL, MZL, or SLL) whose disease is refractory to rituximab and to either chemotherapy or RIT. Approximately 120 subjects will be enrolled. Enrollment is anticipated at approximately 100 sites with approximately 40 sites in the US and the remainder of sites outside of the US. It is anticipated that the entire study will accrue subjects over approximately 30 months.

4.1 SCHEDULE OF ADMINISTRATION

Subjects will receive a starting dose of 25 mg IPI-145 BID over the course of 28-day treatment cycles for up to 13 cycles.

After completing 13 treatment cycles of IPI-145, subjects who have documented evidence of response (CR or PR) or SD at the Cycle 14 Day 1 response assessment according to the revised IWG criteria¹ may continue to receive additional cycles of IPI-145 until disease progression or unacceptable toxicity. Treatment continuation assessments will be made thereafter at the start of every fourth cycle according to [Table 3](#).

4.2 DOSE INTERRUPTION/HOLD/MODIFICATION GUIDELINES

Subjects will be monitored continuously for toxicity while on study treatment. Toxicity will be assessed using the National Cancer Institute Common Terminology Criteria for Adverse Events (NCI-CTCAE) Version 4.03. If a subject has an adverse event at least possibly related to study drug, then dose interruptions/holds with possible modifications should be made according to [Table 6](#) below. Deviations from these guidelines may occur based on the clinical judgment of the Investigator with notification to the Medical Monitor/Sponsor. There should be no attempt to make up for missed doses.

Table 6: Dose Interruption/Hold/Modifications for IPI-145-Related Toxicities

IPI-145-related Toxicities ^{a, b}	Dose Interruption/Hold/Modification/Recommendation for IPI-145 ^c
Non-hematologic: Grade 2 or higher Pneumonitis/Pneumonia Or Grade 3 or higher all other Nonhematologic	First occurrence: Withhold until return to \leq Grade 1 or baseline level; re-challenge therapy at original dose level.
Hematologic: Grade 3 or higher febrile neutropenia Or New Grade 4 neutropenia >7 days duration Or Grade 3 or higher thrombocytopenia with Grade ≥ 2 hemorrhage Or New Grade 4 thrombocytopenia of any duration requiring transfusion support.	Second occurrence of same AE: Withhold until return to \leq Grade 1 or baseline level; re-initiate therapy at one dose level lower from current dose. Third occurrence of same AE: Withhold until return to \leq Grade 1 or baseline level; re-initiate therapy at one dose level lower from current dose. Fourth occurrence of same AE: Discontinue subject from study drug

Recommendations for implementation of dose interruption

Immediate hold for Grade 4 or higher nonhematologic toxicities and Grade 3 or higher febrile neutropenia
For all other events, reduce from BID dosing to QD for two days, then hold

- a. IPI-145 Related = possible, probable, or definite relationship to IPI-145 as defined in [Section 8.2.1](#).
- b. Toxicity grades are defined per CTCAE Version 4.03. Note if parameter is not defined by CTCAE, then AE grading criteria ([Section 8.2.1](#)) should be utilized.
- c. Refer to [Table 7](#) for IPI-145 dose levels.

Treatment Interruption for Nonhematologic Toxicity

Treatment with IPI-145 should be interrupted for the following nonhematologic toxicities:

- Grade 2 or higher pneumonitis/pneumonia, defined as symptomatic and requiring medical intervention, including oral antimicrobials and/or steroids
 - Subjects who develop new pulmonary symptoms (e.g. cough, shortness of breath, dyspnea on exertion) or new radiographic findings should have IPI-145 held and receive empiric antimicrobial coverage while undergoing evaluation. Corticosteroids for symptomatic treatment of pneumonitis is recommended (and allowed per protocol). Restarting treatment with IPI-145 is allowed after complete resolution of symptoms.
- Grade 3 or higher other nonhematologic toxicity including the following:

- Infections: Subjects who develop infections requiring IV antibiotics/antifungals/anti-virals should have IPI-145 held until infection resolves (subject may restart IPI-145 while completing a course of oral therapy). Prophylaxis to prevent recurrence/opportunistic infections will not preclude the subject from restarting treatment.
- Hepatic events: Subjects who develop Grade 3 or higher transaminase (ALT/AST) elevations with or without clinical symptoms should have IPI-145 held until return to \leq Grade 1. Additional work-up to evaluate viral infection/reactivation, exposure to environmental toxins (e.g. alcohol/con-meds), or other causes is recommended before restarting treatment with IPI-145.
- Gastrointestinal: Subjects who develop Grade 3 or higher nausea, vomiting or diarrhea despite optimal treatment should have IPI-145 held until resolution of symptoms. Evaluation of concomitant medications, gastrointestinal infections or inflammatory bowel (via endoscopy and biopsy) should be considered with persistent diarrhea or recurrence with restarting IPI-145. Corticosteroids (budesonide) with taper are allowed if colitis is suspected/cannot be ruled out.
- Skin rash: Subjects who develop Grade 3 or higher skin rashes should have IPI-145 held until return to \leq Grade 1. In the setting of new Grade 1-2 skin rash early intervention is recommended to ameliorate risk of worsening symptoms. Evaluation of concomitant medications, environmental exposure, infections or other contributing factors is recommended.
- Cardiac: Subjects who develop new Grade 3 or higher cardiac events should have IPI-145 held until resolution of symptoms. This includes new Grade 3 QTcF prolongation only if >20 ms increase from Baseline. A new Grade 3 QTcF prolongation (>20 ms from baseline) requires triplicate ECGs with the average measurement used and the use of Fridericia's correction method (QTcF). For subjects with a right or left BBB, a new Grade 3 QTc prolongation is defined as an increase in QTcF of >100 ms from the pre-dose ECG to any post dose ECG as the QRS interval is prolonged at Baseline (by approximately 40 ms) in subjects with a BBB

Subjects requiring treatment interruption should be re-evaluated at least weekly until the toxicity improves to \leq Grade 1 or returns to Baseline level. IPI-145 dose will be restarted at doses described in [Table 7](#).

Treatment Interruption for Hematologic Toxicity

Worsening or transient Grade 3 or higher neutropenia, anemia, and/or thrombocytopenia caused by the subject's existing disease or by IPI-145 are to be expected. Blood counts should be monitored as described in the protocol with the frequency increased as clinically indicated in the setting of new or worsening Grade 3 or higher cytopenias. IPI-145 dosing may be interrupted at any time, at the discretion of the treating physician.

Treatment with IPI-145 should be interrupted for the following symptomatic hematologic toxicities:

- Grade 3 or higher febrile neutropenia
- Grade 3 or higher thrombocytopenia associated with Grade 2 or higher hemorrhage

**Protocol IPI-145-06
IPI-145****Verastem, Inc.**

The subject should be re-evaluated at least weekly until the toxicity improves to \leq Grade 1 or returns to Baseline.

A dose may be withheld up to 42 days for toxicity. Doses withheld for >42 days due to treatment-related toxicity will result in permanent discontinuation from treatment. Any subject who requires reduction to less than 10 mg BID due to repeat occurrence of the same treatment-related toxicity will be permanently discontinued from treatment. Any subject who requires reduction to less than 5 mg BID for different treatment-related toxicities will be permanently discontinued from study treatment. Dose levels are shown in [Table 7](#).

Table 7: IPI-145 Dosing Levels

Dose Level	Dose (mg)
1	25 BID
-1	15 BID
-2	10 BID
-3	5 BID

Subjects who have a dose reduction due to a toxicity may be eligible for a dose increase back to the dose level prior to the reduction (i.e. the starting dose or dose of previous reduction if subject was dose reduced more than one level) if the following criteria are met:

1. Subject has tolerated the lower treatment dose for >1 treatment cycle
2. Subject has recovered to baseline levels from the toxicity which caused the dose reduction

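### Table 6 puts related Grade 2-3 pneumonitis/pneumonia on two days of once-daily dosing before the hold, against the pulmonary instruction in the same section

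*Protocol*

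**What the plan says.** Protocol Section 4.2 directs sites to Table 6 for adverse events at least possibly related to IPI-145. Table 6 lists pneumonitis/pneumonia from Grade 2 upward as a hold trigger; other nonhematologic toxicity triggers a hold only from Grade 3.

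Under Table 6, two lines headed as recommendations say how to start the interruption. The first names the events for which the drug stops at once: "Immediate hold for Grade 4 or higher nonhematologic toxicities and Grade 3 or higher febrile neutropenia". The second covers every trigger that the first leaves out, and lets dosing go on for a short time: "For all other events, reduce from BID dosing to QD for two days, then hold".

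Further down Section 4.2, the text on nonhematologic toxicity describes the pulmonary trigger as "Grade 2 or higher pneumonitis/pneumonia, defined as symptomatic and requiring medical intervention". The bullet beneath it says that subjects with new pulmonary symptoms "or new radiographic findings should have IPI-145 held and receive empiric antimicrobial coverage while undergoing evaluation".

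Two sentences in the section give latitude. One precedes Table 6: "Deviations from these guidelines may occur based on the clinical judgment of the Investigator with notification to the Medical Monitor/Sponsor". The other is in the paragraph on hematologic toxicity: "IPI-145 dosing may be interrupted at any time, at the discretion of the treating physician".

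**The concern.** The two instructions give different answers for the same patient. Pneumonitis/pneumonia is nonhematologic, so at Grade 2 or 3 it misses the immediate-hold line and falls into the residual category, which continues dosing once daily for two days. No pulmonary exception is written. The pulmonary bullet mentions no step-down and ties the hold to the period of evaluation.

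What is at stake is subject safety and uniform conduct across about 100 planned sites. A site following Table 6 would keep giving the suspected drug to someone whose lung event, by the protocol's own description, is symptomatic and needs treatment. The plan is more cautious about these events than about other nonhematologic toxicity, since it acts one grade earlier. Pairing that lower threshold with the slower way of starting a hold works against its purpose.

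**Working it through.** The plan states no figure to reproduce. The check sets the rules side by side and then sizes the difference.

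**Rules applied by grade (related, newly arising pneumonitis/pneumonia)**

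| Grade | Table 6 implementation lines | Pulmonary bullet |
|---|---|---|
| 2 | once daily for two days, then hold | held during evaluation |
| 3 | once daily for two days, then hold | held during evaluation |
| 4 or above | immediate hold | held during evaluation |

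The triggers are not identical. Table 6 needs a graded, related event; the bullet needs only new symptoms or findings. Because Grade 2 or higher is described as symptomatic, a new related Grade 2-3 case will usually meet both.

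**Extra drug per event**

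Doses given in the step-down = 2 days x 1 dose per day = 2. With the dose levels in Table 7:

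- 25 mg level: 2 x 25 = 50 mg
- 15 mg level: 2 x 15 = 30 mg
- 10 mg level: 2 x 10 = 20 mg
- 5 mg level: 2 x 5 = 10 mg

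These are upper limits. If the day of recognition counts as the first once-daily day, one of the two doses may already have been taken.

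**Extra exposure at 25 mg**

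Protocol Section 1.3.3.2 reports that, after repeat dosing at 25 mg BID, mean Cmax and AUC0-12 "values are 1460 ng/mL and 8129 ng*h/mL, respectively". It also says that AUC0-12 is proportional to dose. Assuming linear pharmacokinetics, each dose contributes one steady-state AUC0-12:

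2 x 8129 = 16,258 ng*h/mL, the same as one day of BID dosing.

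**Washout after an immediate hold**

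The same section says the mean half-life "was 4.5 hours following 25 mg BID administration". Fraction remaining = 2^(-t / half-life):

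- 24 h: 2^(-24/4.5) = 2.5%
- 48 h: 2^(-48/4.5) = 0.06%

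The first-in-human study in healthy subjects (Section 1.3.3.1) gives mean half-lives of 6.5 to 11.7 h after repeat dosing. With those, the 24 h fraction is 2^(-24/6.5) = 8% to 2^(-24/11.7) = 24%. Under the step-down, the last dose itself can come up to 48 h after the decision to interrupt.

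**Context only**

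Section 1.3.3.2 reports related Grade 3 or higher pneumonitis in 6% of 32 Phase 1 iNHL subjects. Since 1/32 = 3.1%, 2/32 = 6.25% and 3/32 = 9.4%, that is 2 subjects. The figure pools doses, omits Grade 2 and includes any Grade 4 case, so it does not estimate how many subjects here would receive extra drug.

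**The case against.** The strongest counter-reading is that the two texts do different jobs: Section 4.2 says which events are held, and the Table 6 lines say how. The bullet says held, not held at once. The same verb appears in the bullets for Grade 3 hepatic, gastrointestinal, rash and cardiac events, all of which also go through the step-down. That reading works for those bullets, where the hold is defined by its end point (recovery of the toxicity). It does not work for the pulmonary bullet, where the hold is to be in force while the evaluation is under way. Two days of dosing at the start of that evaluation cannot be squared with it.

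A second argument is that the bullet acts first, on symptoms or imaging, before grading or attribution. A compliant site would have stopped already and have nothing left to step down. This stands as a limit on how often the problem bites: extra dosing arises only where a site works from Table 6. It does not settle which instruction that site should follow.

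A third argument is latitude. The lines are recommendations, deviations are allowed with notification, dosing may be interrupted at any time, and Section 7.2.1 again allows investigator judgment on dose reductions and discontinuations. An immediate hold is therefore always permitted. But permission to depart from a default does not correct the default.

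It is also fair to say that no harm is demonstrated. The Phase 1 list of related Grade 3 or higher events for the 15 iNHL subjects at 25 mg BID names only ALT/AST elevation, although that list is evidently not complete.

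**Conclusion.** The concern holds. As written, Table 6 sends related Grade 2-3 pneumonitis/pneumonia to a two-day step-down, the pulmonary bullet has the drug held during evaluation, and no text gives precedence. The cost of following Table 6 is at most two further doses per event: 50 mg and about 16,258 ng*h/mL at the starting dose level.

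The exposure figure assumes linear pharmacokinetics and that neither dose had been taken when the event was recognised. The number of subjects affected cannot be estimated from the documents, and an effect of the extra doses on the course of an event is not shown. The ORR test, sample size and error rates are untouched. This is a safety instruction that should be corrected because it contradicts the protocol's own pulmonary rule and is cheap to put right.

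**What to change.** Amend the immediate-hold line under Table 6 so that it covers three groups: pneumonitis/pneumonia of Grade 2 or above; any other nonhematologic toxicity of Grade 4 or above; and febrile neutropenia of Grade 3 or above. Leave the pulmonary text in Section 4.2 and the step-down for the remaining events as they are. Drug taken between the decision to interrupt a related Grade 2-3 pulmonary event and the hold then falls from up to two doses to none.

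The cost is one line in a protocol amendment, with no added procedures, visits or data and no change to the SAP.
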